14. ADMINISTRATIVE, LEGAL, AND ETHICAL ASPECTS

14.1 Conduct of the Trial

The trial will be conducted according to the protocol, the ICH Consolidated Guideline for Good Clinical Practice (ICH GCP E6 (R2) - March 2018), and the applicable regulatory requirements.

14.2 Ethical Principles

The study has to be conducted in accordance with the principles of the Declaration of Helsinki (1964), as amended or clarified by the General Assembly of the World Medical Association (World Medical Association Declaration of Helsinki, last amended October 2013).

14.3 Health Authorities and Institutional Review Board (IRB)

This study is to be conducted in accordance with IRB regulations (U.S. 21 CFR Part 56).

The study protocol and subject informed consent form must be submitted to the appropriate properly constituted IRB. The approval from the IRB must refer to the exact protocol title and number, and identify all documents reviewed and their corresponding versions. A list of the IRB review board members as well as a statement of compliance with GCP and applicable laws and regulations should be also provided. Copies of all IRB correspondence with the Investigator should be given to the company representing Nicox.

The company representing Nicox is to be notified immediately if the responsible IRB has been disqualified or if proceedings leading to disqualification have begun.

The Principal Investigator is also responsible for providing the IRB with safety reports of any unexpected SAEs from any clinical study conducted with the study medication, as dictated by the IRB requirements. These safety reports will be provided to the Principal Investigator by the company representing Nicox.

The Principal Investigator is responsible for informing the IRB of any amendment to the protocol. In addition, the IRB must approve all materials used to recruit subjects for the study. Either the Principal Investigator, or the company representing Nicox, must submit progress reports to the IRB according to the IRB requirements and local regulations and guidelines. The Principal Investigator must also provide the IRB with any reports of Serious Adverse Events from the study site, as dictated by the IRB requirements.

14.4 Subject Information and Consent

It is the responsibility of the Investigator to obtain written and signed informed consent prior to enrollment into the study (i.e., at the Screening Visit) and before any procedure related to the trial is performed.

The methods of obtaining and documenting informed consent and the contents of the ICF will comply with ICH GCP guidelines, the requirements of 21 CFR Part 50 "Protection of Human Subjects", the Health Insurance Portability and Accountability Act (HIPAA) regulations, and all other applicable regulatory requirements.

The Investigator or their designee must fully explain and adequately inform the subject of the purpose of the study prior to entering a subject into the clinical trial or performing any trial-specific procedures.

Once the subject fully agrees to participate in this study, written ICF must be documented by the subject's personally dated signature and the personally dated signature of the informing Investigator/designated person conducting the informed consent discussion. The subject will receive one copy and the original ICF will be filed in the subject study file on site.

The dates when the written informed consent was obtained for the subject and when the subject withdraws or exits the study, must be documented in the subject source documents so that it is known if the subject is currently participating in a clinical study.

In signing the ICF, a subject accepts direct access to their data by Nicox, the company representing Nicox, monitor, auditor, and Health Authority representatives.

14.5 Confidentiality Regarding Trial Subjects Data

In order to maintain subjects' privacy, all study materials will identify subjects in a fully anonymized manner. The Investigator will grant the company or its designated representatives, or regulatory authorities the right to access subject's original medical records for verification of the data gathered in the study. Subject's confidentiality will be maintained and will not be made publically available unless mandated by applicable laws and regulations.

14.6 Archiving at the End of the Study

After the close-out visit at each site, the study is considered completed. A copy of the final completed CRFs will be stored in the Investigator's archives for up 2 years following the final approval of the last marketing authorization, together with all the other site study-specific documents (including Investigator's site file). Neither of these is ever transferred to the Sponsor.

All study-related materials must be stored in a secure manner and must remain available upon request from Nicox or any Health Authority.

15. PUBLICATION POLICY

The institutions, investigators, and all study personnel shall regard all study data as confidential until analyses and review of the analyses are performed by Nicox.

The institutions and investigators participating in this trial shall have no right to publish or present the results of this study without the prior written consent of Nicox.



Tan M-H, Lebwohl M, Esser AC, Wei H. The penetration of 0.005% fluticasone propionate ointment in eyelid skin. *J Am Acad Dermatol.* 2001;45(3):392-6.

United States Prescribing Information for Cutivate Lotion, 2015.

United States Prescribing Information for Fluticasone Propionate Cream, USP 0.05%. 2016.

APPENDIX 1: TIME AND EVENTS TABLE – Cohorts 1 & 2

	Screening Visit ^a (day -7 to -3)	Baseline/ Day 1 Visit	Day 4 Visit (± 1 day)	Day 8 Visit (± 1 day)	Day 11 Visit (± 1 day)	Day 14 Visit (- 1 day)	Day 28/ Exit Visit (± 2 days)
Informed Consent/HIPAA	X	-	-	-	-	-	-
Screening Number and Registration	X	-	-	-	-	-	-
Demographics	X	-	-	-	-	-	-
Medical/Ophthalmic History & Update	X	X	X	X	X	X	X
Concomitant Medications	X	X	X	X	X	X	X
Urine Pregnancy Test	X	-	-	-	-	X	-
[REDACTED]	X	X	-	X	X	X	X
Best Corrected Visual Acuity (ETDRS)	X	X	X	X	X	X	X
Eyelid Evaluation	X	-	-	-	-	-	-
Eyelid Evaluation [REDACTED]	-	X	X	X	X	X	X
Slit Lamp Biomicroscopy	X	X	X	X	X	X	X
[REDACTED]	X	X	X	X	X	X	X
[REDACTED]	X	X	-	-	-	X	-
[REDACTED]	X	X	-	X	X	X	X
[REDACTED]	X	X	-	X	X	X	X
[REDACTED]	X	X	-	X	X	X	X
IOP	X	X	X	X	X	X	X
Eyelid Scrubs ^b	[REDACTED]	-	X	X	X	X	X
Study Medication Application [REDACTED]	-	X ^c	X	X	X	X	-
Eyelid Evaluation [REDACTED]	-	X ^d	X	X	X	X	X ^d
Eyelid Evaluation [REDACTED]							X ^e
[REDACTED]	X	X	-	-	-	X	-
Dilated Ophthalmoscopy	X	-	-	-	-	-	X
Inclusion/Exclusion Criteria	X	X	-	-	-	-	-
Randomization	-	X	-	-	-	-	-
Dispense study medication, study related material, diary and instructions	-	X	-	-	-	-	-
Review of subject diary	-	-	X	X	X	X	-
Collection of study medication and diary	-	-	-	-	-	X	-
Eyelid Scrub & Study Medication Application Training	-	X	-	-	-	-	-
Adverse Event Query	X	X	X	X	X	X	X

Study Exit	-	-	-	-	-	-	-	-	X
------------	---	---	---	---	---	---	---	---	---

- a) Screening Visit may be performed at any time of the day. All other visits will be performed in the morning with specific time points for certain assessments.
- b) Daily eyelid scrubs will be performed prior to study medication application by the subject when self-administering study treatment. On study visit days eyelid scrubs and morning study medication application will be performed by the subject under the supervision of the study staff.
- c) At the Baseline/Day 1 Visit, study medication is administered after Eyelid Evaluation [REDACTED] and final confirmation of Eligibility and randomization. Subjects will be instructed on proper application technique. Refer to [Section 7.2](#) for detailed order of assessments.

[figure not shown]
f) Subject-rated [REDACTED] will be assessed prior to investigator-evaluated [REDACTED]

[figure not shown]
APPENDIX 2: METHODS OF CLINICAL EVALUATION

For all assessments, sites should use the same instrument(s), method and examiner whenever possible throughout the study. All ophthalmic assessments will be performed bilaterally. The right eye will be assessed first, then the left eye.

1. URINE PREGNANCY TEST

Urine pregnancy test is to be conducted on site by study staff per the instructions on the pregnancy kit.

3. 

4. BEST CORRECTED VISUAL ACUITY (BCVA)

Best corrected visual acuity (BCVA) will be measured by trained personnel prior to slit-lamp examination and dilating the eyes with the subject wearing their habitual correction or with pinhole refraction.

Equipment

Visual acuity will be assessed: using the following equipment:

- ETDRS illuminator cabinet - wall mounted or with the appropriate stand
- ETDRS Chart 1 for the Right Eye (4 m)
- ETDRS Chart 2 for the Left Eye (4 m)

Illumination of the ETDRS Illuminator Cabinet and Room Illumination

The internal illumination of the ETDRS illuminator cabinet should be turned on. This will provide the nominal contrast for each of the charts. **Room illumination should be turned off**, to ensure that the illumination is consistent for each measurement. Ambient sources of light in the room should be kept at a minimum. The room lighting and any ambient sources should be consistent in their use and placement at each subject visit throughout the course of this study.

Measurement

Testing of both eyes is done at a distance of **4 meters** from the VA chart. The chart should be at a comfortable viewing angle. The right eye (chart 1) will be tested first then the left eye (chart 2). The eye not being tested will be properly occluded.

The subject should be told that the chart contains only letters and no numbers. If the subject reads a number, he/she should be reminded that the chart contains no numbers and the examiner should then request a letter in lieu of the number.

Beginning with the right eye, the subject should be asked to read slowly, so as to achieve the best identification of each letter. He/she is not to proceed to the next letter until he/she has given a definite response. If the subject changes a response (e.g., 'that was a "C" not an "O"') before he has read aloud the next letter, then the change must be accepted. If the subject changes a response having read the next letter, then the change is not to be accepted. The examiner should never point to the chart or to specific letters on the chart during the test.

A maximum effort should be made to identify each letter on the chart. When the subject says he or she cannot read a letter, he or she should be encouraged to guess. If the subject identifies a letter as one of two letters, he or she should be asked to choose one letter and, if necessary, to guess. When it becomes evident that no further meaningful readings can be made, despite encouragement to read or guess, the examiner should stop the test for that eye. However, **all letters on the last line should be attempted** as letter difficulties vary and the last may be the only one read correctly. The number of letters missed or read incorrectly should be noted.

Repeat the aforementioned measurement technique for the left eye with the right eye occluded.

Recording and Scoring logMAR Visual Acuity

Letters that are INCORRECT will be noted and totaled in each line. The last line in which a letter was read correctly will be taken as the base logMAR value. The total number of letters read incorrectly will be the (n) value which will be multiplied by 0.02 to obtain the (T) value. To calculate the logMAR VA score the base logMAR and (T) values will be added.

Example -Subject reads the following:

- 1 letter INCORRECT on 0.2 line
- 3 letters INCORRECT on line 0.1
- All letters before line 0.2 were read correctly

Base logMAR (last line in which a letter was read correctly)	= 0.1
n (total number of letters INCORRECT)	= 4
T = n X 0.02	= 0.08 (4 x 0.02)
logMAR VA Score = Base logMAR + T	= 0.18 (0.1 + 0.08)

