4.3 Inclusion Criteria

Prior to inclusion in the study, each subject must fulfill all of the following criteria:

- 1) be at least 18 years of age;
- 2) have a documented history of blepharitis of at least 6 months;
- 3) be currently experiencing an acute exacerbation of blepharitis [REDACTED]
[REDACTED] at both the Screening and Baseline/Day 1 Visits;
- 4) have a Best Corrected Visual Acuity (BCVA) of +0.60 logMAR (approximately 20/80 Snellen) or better in each eye as measured using an EDTRS chart with the subject wearing their habitual correction or with pinhole refraction;
- 5) be able to perform eyelid scrubs with diluted baby shampoo and apply study medication satisfactorily;
- 6) if female, must either be incapable of pregnancy because of hysterectomy, bilateral tubal ligation, or bilateral oophorectomy, or be post-menopausal (have been amenorrheic for at least 2 years) or must use an effective method of birth control for the duration of the study. Female subjects of childbearing potential must have a negative urine pregnancy test and not be breastfeeding or planning a pregnancy;
- 7) be able to provide written informed consent and sign the HIPAA form to participate in the study, in accordance with the International Council for Harmonisation (ICH) Good Clinical Practice (GCP) guidelines and local regulations, before initiating any study-related procedures; and
- 8) be able and willing to comply with treatment and all study procedures.

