15.2 Best Corrected Visual Acuity

Best corrected visual acuity will be measured by trained personnel prior to slit-lamp examination and dilating the eyes with the subject wearing their habitual correction or with pinhole refraction.

Testing of both eyes is done at a distance of 4 meters from the visual acuity ETDRS (Early Treatment of Diabetic Retinopathy Study) chart. The chart should be at a comfortable viewing angle. The right eye (chart 1) will be tested first then the left eye (chart 2). The eye not being tested will be properly occluded.

The observed and change from baseline BCVA will be summarized using continuous descriptive statistics by visit for each treatment group and for all actively treated subjects. A subject listing of BCVA will be

produced. [REDACTED]

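### The written logMAR scoring rule counts errors on lines below the base line, so each fully failed line that is counted makes BCVA 0.10 too high

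*Protocol*

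**What the plan says.** The scoring rule is in Protocol Appendix 2, section 4, under the recording and scoring of logMAR acuity. It has four parts:

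- Recording: "Letters that are INCORRECT will be noted and totaled in each line".
- Base: "The last line in which a letter was read correctly will be taken as the base logMAR value".
- Penalty: "The total number of letters read incorrectly will be the (n) value which will be multiplied by 0.02 to obtain the (T) value".
- Score: "To calculate the logMAR VA score the base logMAR and (T) values will be added".

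The single worked example has 1 error on line 0.2 and 3 errors on line 0.1, and gives 0.18. It mentions no line below 0.1.

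The measurement text in the same section asks for maximum effort and for guessing. On ending the test of an eye it says: "When it becomes evident that no further meaningful readings can be made, despite encouragement to read or guess, the examiner should stop the test for" (the eye under test). It adds that "all letters on the last line should be attempted". No fixed stopping line is set.

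The score is used in two places. Inclusion criterion 4 (Protocol section 4.3) requires a subject to "have a Best Corrected Visual Acuity (BCVA) of +0.60 logMAR (approximately 20/80 Snellen) or better in each eye". BCVA is also a named safety measure (Protocol section 2.4, SAP section 2.3), and SAP section 15.2 states: "The observed and change from baseline BCVA will be summarized using continuous descriptive statistics by visit". The visible text of SAP section 15.2 gives no scoring rule. The end of that section is blacked out, so it is not known whether more is said there.

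**The concern.** The base and the penalty do not cover the same lines. The base stops at the lowest line with a correct letter, whereas n takes in every error on every line attempted. An eye that tries one more line and reads none of it gets no credit for that line but is charged for all of its letters.

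The case is foreseeable. Subjects are urged to guess, and the last line is to be attempted in full because a single letter on it may be the only one read. A last line with no letter read is the adjacent outcome.

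Two uses of BCVA are exposed. The first is the safety summary of change from baseline, in arms of about 5 to 10 subjects, for a steroid whose stated risks (Protocol section 1.3) include loss of acuity. The second is the entry limit of +0.60.

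**Working it through.** **Inputs**

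- Base, n, 0.02 per letter and the sum of base and T: Protocol Appendix 2, section 4.
- Example eye: 1 error on line 0.2, 3 errors on line 0.1, all earlier lines correct (same section).
- Entry limit +0.60: Protocol section 4.3.
- Arm sizes of about 5 to 10: Protocol section 3.1.
- Assumption: 5 letters per line. The documents do not state it, but it follows from the line step and the letter value: 0.1 / 0.02 = 5.
- Assumption, for the letter-count check only: the chart's top line is 1.0, so score = 1.10 − 0.02 × letters correct.

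**Step 1. Reproduce the protocol's figure**

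Base 0.1, n = 1 + 3 = 4, score = 0.1 + 4 × 0.02 = 0.18, as printed. Letter count: 8 full lines from 1.0 to 0.3 give 40, plus 4 and 2 makes 46. Then 1.10 − 46 × 0.02 = 0.18. The two agree.

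**Step 2. Extend the same eye below line 0.1**

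| What happens below line 0.1 | Rule as written | n limited to lines down to the base | Letter count |
|---|---|---|---|
| Nothing attempted | 0.1 + 4 × 0.02 = 0.18 | 0.18 | 0.18 |
| Line 0.0, 1 of 5 correct | 0.0 + 8 × 0.02 = 0.16 | 0.16 | 0.16 |
| Line 0.0, 0 of 5 correct | 0.1 + 9 × 0.02 = 0.28 | 0.18 | 0.18 |
| Lines 0.0 and −0.1, none correct | 0.1 + 14 × 0.02 = 0.38 | 0.18 | 0.18 |

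The limited rule matches the letter count in every row. The rule as written departs from it by 5 × 0.02 = 0.10 for each fully failed line. It is also discontinuous: on line 0.0, one letter moves the score by 0.28 − 0.16 = 0.12, when one letter is worth 0.02.

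**Step 3. Change from baseline**

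Error in change = 0.10 × (counted failed lines at follow-up − counted failed lines at baseline). None then one gives a false loss of 0.10. One then none gives a false gain of 0.10. Equal numbers cancel.

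For one affected study eye, the arm mean change moves by 0.10 / 10 = 0.01 in an arm of 10, or 0.10 / 5 = 0.02 in an arm of 5. An individual value, and hence possibly the minimum or maximum, moves by the full 0.10.

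**Step 4. Entry limit**

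An eye that reads line 0.6 cleanly and fails all of line 0.5 is recorded as 0.6 + 5 × 0.02 = 0.70 instead of 0.60. With one counted failed line, eyes truly at or below 0.60 exceed the limit only if true score + 0.10 > 0.60. In steps of 0.02 these are 0.52, 0.54, 0.56, 0.58 and 0.60, recorded as 0.62 to 0.70. The error can only exclude an eye, never admit one.

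**The case against.** The strongest reply is that this is a gap in wording, not an operating error. The only worked example stops at the base line and gives the right answer. BCVA is measured by trained personnel, and Appendix 2 asks for the same method and examiner whenever possible, which reduces variation between visits. Consistent practice largely cancels in change scores. The summaries are descriptive, there are no formal hypotheses, and allocation is randomised and masked, so scoring noise should not favour an arm. Slit lamp, IOP, fundus examination and adverse events also cover ocular safety.

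Most of this stands, and it limits the consequence. It does not remove the defect: the example contains no failed line, so it cannot tell an examiner whether to count one, and the sentence defining n says to count all errors. If some examiners follow the text and others stop at the base, sites will score differently.

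Three stronger readings are tempting but not supported:

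- A reader might infer that many tests are affected. Any frequency would depend on how sharply letter reading falls off, how often guesses succeed and when examiners stop. The documents give none of these.
- A reader might infer that recorded scores are wrong, or that every eye truly at 0.52 to 0.60 fails entry. Both need a failed line that was attempted and also counted.
- A reader might infer that a declined letter is scored as correct, because the measurement text speaks of letters missed or read incorrectly while n names only those read incorrectly. A definite response is required for each letter and guessing is encouraged, and an unread letter may naturally be taken as incorrect. The wording is ambiguous, not plainly wrong. If declined letters were left out of n, a failed line would add less than 0.10.

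**Conclusion.** The point holds as a defect in the written rule. A rule that is followed exactly, in a situation the protocol's own test instructions make likely to arise, should not give 0.28 for an eye whose letter count gives 0.18.

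The size is 0.10 logMAR per counted failed line. This rests on 5 letters per line and on an examiner who counts the failed line in full. Change from baseline is affected only when the number of counted failed lines differs between visits, in either direction. With one counted failed line, the entry limit is affected only for eyes truly at 0.52 to 0.60, toward exclusion. How often either occurs cannot be determined from the documents. The correction is worth making because it is cheap and improves a named safety measure and an entry threshold. It gives no ground for saying that the trial's BCVA data are unreliable.

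**What to change.** In Protocol Appendix 2, section 4, define n as the number of letters missed or read incorrectly on all lines down to and including the base line, and state that lines below the base line are not counted. Add a second worked example with a failed line: 1 error on 0.2, 3 on 0.1 and 5 on 0.0, scoring 0.18. Notify the sites, and state the same rule in SAP section 15.2 if the blacked-out text does not already do so.

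For values already recorded, use the per-line error totals in source, where kept, to check whether failed lines were counted. Do this for all subjects in both cohorts by the same rule, with the checker masked to treatment. If failed lines were counted, report the rescored BCVA as a documented sensitivity summary and do not overwrite locked Cohort 1 data. Cohort 1 has an interim analysis, SAP sections 1 and 8.4 describe the remaining unmasking as that of Cohort 2, and SAP section 6.1 requires sponsor approval for changes after lock.

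The cost is a small protocol amendment, with the sponsor approval and IRB review that Protocol section 13.9 requires unless the change counts as logistical or administrative, plus a source check. No visit or procedure is added.

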5. EYELID EVALUATION

[figure not shown]
[figure not shown]
The Eyelid Evaluations will be performed bilaterally (upper and lower eyelids) at each specified visit.

Eyelid discomfort will be evaluated prior to investigator evaluation of eyelid margin redness and eyelid debris.

5.1 Subject-Evaluated Symptoms

Eyelid Discomfort Scale		
		
0	=	No
1	=	Mild
2	=	Moderate
3	=	Severe
		

5.2 Investigator-Evaluated Signs

[figure not shown]

6. SLIT LAMP EXAMINATION

The slit lamp examination will be performed prior to any contact assessments and instillation of any drops at each specified visit and at the discretion of the Investigator.

Each structure will be graded as 

The following structures will be examined at each visit:

- Eyelid 
- Conjunctiva 
- Cornea
- Lens
- Iris/Pupil
- Anterior Chamber

7. [REDACTED]

Conjunctival Redness Scale				
None	0	=	[REDACTED]	[REDACTED]
[REDACTED]	[REDACTED]	=	[REDACTED]	[REDACTED]
[REDACTED]	[REDACTED]	=	[REDACTED]	[REDACTED]
[REDACTED]	[REDACTED]	=	[REDACTED]	[REDACTED]
Severe	4	=	[REDACTED]	[REDACTED]
[REDACTED]				

[figure not shown]
[REDACTED]
The examiner will instill [REDACTED]

For each eye, [REDACTED]

If sodium fluorescein solution has not already [REDACTED]

ty g g.

[REDACTED]			
[REDACTED]			
[REDACTED]	[REDACTED]	=	[REDACTED]
[REDACTED]	[REDACTED]	=	[REDACTED]
[REDACTED]	[REDACTED]	=	[REDACTED]
Severe	4	=	[REDACTED]
[REDACTED]			

[figure not shown]

[figure not shown]
[REDACTED]	[REDACTED]	[REDACTED]
A - [REDACTED]	[REDACTED]	[REDACTED]
	[REDACTED]	[REDACTED]

[REDACTED]
 [REDACTED]
 [REDACTED]

[REDACTED] 1 times to distribute the lissamine green.

Staining				
		=		
		=		
		=		
Severe	4	=	c	

At the slit-lamp with the subject looking in upward gaze, [REDACTED]

Eyelid Margin	
	[REDACTED]
	[REDACTED]
	Moderate [REDACTED]
	Severe [REDACTED]
	Very severe [REDACTED]

[REDACTED]		
0	Normal	[REDACTED]
	[REDACTED]	[REDACTED]

0	Normal	
1		
2		
3		
4		

0	
1	
2	
3	
4	

Meibomian gland function

Meibomian Gland		
3	=	
2	=	
1	=	
0	=	

Digital photographs of the eyes will be obtained at the slit lamp. [REDACTED]

